## 9.4 Safety Oversight Committee (SOC)

The Duke Cancer Institute SOC is responsible for annual data and safety monitoring of DUHS sponsor-investigator Phase I and II, therapeutic interventional studies that do not have an independent Data Safety Monitoring Board (DSMB). The primary focus of the SOC is review of safety data, toxicities, and new information that may affect subject safety or efficacy. Annual safety reviews include, but may not be limited to, review of safety data, enrollment status, stopping rules if applicable, accrual, toxicities, reference literature, and interim analyses as provided by the sponsor-investigator. The SOC in concert with the DCI Monitoring Team (see **Section 10.1** for Monitoring Team description) oversees the conduct of DUHS cancer-related, sponsor-investigator therapeutic intervention and prevention intervention studies that do not have an external monitoring plan, ensuring subject safety and that the protocol is conducted, recorded and reported in accordance with the protocol, standard operating procedures (SOPs), Good Clinical Practice (GCP), and applicable regulatory requirements.

# 10 QUALITY CONTROL AND QUALITY ASSURANCE

## 10.1 DCI Monitoring Team

The Duke Cancer Institute (DCI) Monitoring Team will conduct monitoring visits to ensure subject safety and that the protocol is conducted, recorded, and reported in accordance with the protocol, standard operating procedures, good clinical practice, and applicable regulatory requirements. As specified in the DCI Data and Safety Monitoring Plan, the DCI Monitoring Team will conduct routine monitoring after the third subject is enrolled, followed by annual monitoring of 1 – 3 subjects until the study is closed to enrollment and subjects are no longer receiving study interventions that are more than minimal risk.

Additional monitoring may be prompted by findings from monitoring visits, unexpected frequency of serious and/or unexpected toxicities, or other concerns and may be initiated upon request of DUHS and DCI leadership, the DCI Cancer Protocol Committee, Duke Clinical Trials Quality Assurance (CTQA), the Safety Oversight Committee (SOC), the Sponsor-Investigator, the site's Principal Investigator, or the IRB. All study documents must be made available upon request to the DCI Monitoring Team and other authorized regulatory authorities, including, but not limited to, the National Institute of Health, National Cancer Institute, and the FDA. Every reasonable effort will be made to maintain confidentiality during study monitoring.

## 10.2 Data Management and Processing

### 10.2.1 Study Documentation

Study documentation includes, but is not limited to, source documents, case report forms, monitoring logs, appointment schedules, study team correspondence with sponsors or regulatory bodies/committees, and regulatory documents that can be found in the DCI-mandated "Regulatory Binder" that includes, but is not limited to, signed protocol and amendments, approved and signed informed consent forms, FDA Form 1572, CAP and CLIA laboratory certifications, and clinical supplies receipts and distribution records.

Source documents are original records that contain source data that is all information in original records of clinical findings, observations, or other activities in a clinical trial necessary for the reconstruction and evaluation of the trial. Source documents include, but are not limited to, hospital records, clinical and office charts, laboratory notes, memoranda, subjects' diaries or evaluation checklists, pharmacy dispensing records, recorded data from automated instruments, copies or transcriptions certified after verification as being accurate copies, microfiches, photographic negatives, microfilm or magnetic media, X-rays, subject files, and records kept at the pharmacy, at the

laboratories, and at medico-technical departments involved in the clinical trial. When possible, the original record should be retained as the source document. However, a photocopy is acceptable provided that it is a clear, legible, and an exact duplication of the original document.

#### **10.2.2 Case Report Forms (CRFs)**

The electronic CRF will be the primary data collection document for the study and will be updated in a timely manner following acquisition of new source data. Only the research staff members listed on the delegation of authority log are permitted to make entries, changes, or corrections in the CRF.

An audit trail will be maintained automatically by the electronic CRF management system (eCRF). All users of this system will complete user training, as required or appropriate per regulations.

#### **10.2.3 Data Management Procedures and Data Verification**

Completeness of entered data will be checked automatically by the eCRF system, and users will be alerted to the presence of data inconsistencies. Additionally, queries may be issued by the study data manager or project leader. Missing or implausible data will be queried for completion or correction (i.e., confirmation of data, correction of data, and completion or confirmation that data is not available, etc.).

The database will be reviewed and discussed prior to database closure, and will be closed only after resolution of all remaining queries. An audit trail will be kept of all subsequent changes to the data.

#### **10.2.4 Study Closure**

Following completion of the studies, the PI will be responsible for ensuring the following activities:

- Data clarification and/or resolution
- Accounting, reconciliation, and destruction/return of used and unused study drugs
- Review of site study records for completeness
- Shipment of all remaining laboratory samples to the designated laboratories (i.e., [name] Lab at Duke)

### **11 STATISTICAL METHODS AND DATA ANALYSIS**

All statistical analysis will be performed under the direction of the statistician designated in key personnel. Any data analysis carried out independently by the investigator must be approved by the statistician before publication or presentation.

#### **11.1 Analysis Sets**

The intent-to-treat (ITT) population will consist of all randomized patients. The modified intent-to-treat (ITT) population will consist of all randomized patients who have both a baseline and after week 12 evaluation. In the ITT analyses and the modified ITT analyses patients will be analyzed according to the study arm to which they were randomized. The modified ITT population will be the primary analysis population.

The per-protocol population will consist of all randomized patients with both baseline and after week 12 measurements for the primary endpoint and prior to any analysis: have been deemed compliant and properly evaluated for efficacy per investigator, satisfied all inclusion and exclusion criteria, and correctly assigned treatment.

The safety population will be all patients with at least one safety evaluation.

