### **5.6 Definition of Evaluable Subjects**

For the primary analysis of change in VO2peak, patients with measurements at baseline and after 12 weeks are evaluable.

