### 11.4.2 Statistical Hypothesis, Model, and Method of Analysis

The primary analysis will be checking if there is a significant change in peak oxygen uptake (VO2 peak) from baseline to through week 12 for each schedule, using a paired t-test. The primary analysis will be done for complete cases, (i.e., patients with VO2peak measured at baseline and after week 12) in the ITT population.

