## 11.5 Secondary and Exploratory Objectives

For subjects with VO2 peak measures at week 4 or week 5, descriptive statistics including mean, standard deviation, minimum and maximum of VO2peak changes from baseline to week 4 and to week 5 will also be reported to assess early effects of each sunitinib schedule. Descriptive statistics for other secondary and exploratory endpoints will also be reported for each sunitinib schedule.

In addition, a random effects model will be used to assess the effect of different sunitinib schedules on the VO2 peak change. In the model repeated measurements of VO2 peak change at week 4, 5 and through week 12 from baseline are outcomes, schedule indicator (0 for schedule 4/2, 1 for schedule 2/1) is chosen as the main factor, baseline VO2 peak value and patient characteristics are other included covariates. Similarly, random effects models with other continuous repeated measures (i.e., resting and stress cardiac function and muscle strength) as dependent variables will also be used to analyze the schedule effects.

Sensitivity analyses will be performed for the primary endpoint and key secondary endpoint using Last Value Carried Forward (LOCF) methods. The intent of this sensitivity analysis is to assay the robustness of results observed in the modified ITT population.

Eligibility rate, acceptance rate and adverse event rate will be reported descriptively.

Eligibility rate is defined as the number of subjects eligible for the study divided by the number approached for the study (i.e., screen fail rate).

Acceptance rate is defined as the number of patients agreeing to participate divided by total number randomized.

Rates of adverse events, classified by CTCAE v4.0, will be displayed by body system and preferred term for each arm.

For analysis of the plasma angiome multiplex ELISA data, correlations among analytes will be evaluated by Spearman analysis. Analyte levels at baseline and changes on-treatment will be correlated with baseline VO2peak and changes in VO2peak, respectively.

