## 11.6 Sample Size Calculation

The primary purpose of this study is to check if changes in cardiopulmonary function (VO2peak) in patients from baseline to through week 12 is significant for each sunitinib schedules.

This is a pilot study in which 15 evaluable patients per arm will be randomized with equal probability to either the sunitinib 4/2 or 2/1 schedule. The estimated variance based on a previous pilot study is 3.2 ([name]; unpublished data).

Assuming 1) the same variance at baseline and 12 weeks, and 2) no correlation between the two VO2peak measurements at baseline and 12 weeks, based on 2-sided, paired t-test with 15 patients, the VO2peak mean difference of 2.0 ml kg min from baseline to after 12 weeks can be detected with 80% power and significance level 0.05. If we assume a correlation of 0.20 between the two VO2peak measurements, then the VO2peak mean difference of 1.8 ml kg min from baseline to after 12 weeks can be detected. **Note:** Because VO2peak typically declines by only about 1% per year in adults, this magnitude of decline is believed to be clinically significant.

Because 1) the primary endpoint is mean difference in VO2peak at after 12 weeks) 30 total patients are required for adequate evaluation, patients who are not able to undergo CPET for determination of VO2peak at after 12 weeks will be replaced. We estimate a 20% dropout rate so that 36 patients will need to be accrued in order to have 30 total evaluable patients (15 evaluable in each arm).

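### LOCF, the only named check on the complete-case VO2peak change, says little about the patients who are lost

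*Combined protocol and SAP*

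**What the plan says.** Section 11.1 makes the modified ITT set primary: "The modified intent-to-treat (ITT) population will consist of all randomized patients who have both a baseline and after week 12 evaluation". Section 11.4.2 confirms it: "The primary analysis will be done for complete cases". The choice is declared openly in Section 5.6, where "patients with measurements at baseline and after 12 weeks are evaluable" for the primary analysis.

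Section 11.6 says that "patients who are not able to undergo CPET for determination of" VO2peak after 12 weeks will be replaced, and adds: "We estimate a 20% dropout rate so that 36 patients will need to be accrued".

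For robustness, Section 11.5 states: "Sensitivity analyses will be performed for the primary endpoint and key secondary endpoint using Last Value Carried Forward (LOCF) methods". Its purpose follows: "The intent of this sensitivity analysis is to assay the robustness of results observed in the modified ITT population". The same section plans a random effects model for change in VO2peak, in which "schedule indicator (0 for schedule 4/2, 1 for schedule 2/1) is chosen as the main factor". The contents page lists a Section 11.4.3 on missing data and discontinuation, but the body runs from 11.4.2 straight to 11.5.

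Table 3 places CPET at baseline, Day 29 (schedule 4/2) or Day 36 (schedule 2/1), and Day 85. Rest/exercise echo and muscle CSA appear only at baseline and Day 85. The End of Treatment Visit column has no CPET. Section 8.7 sets that visit about 30 days after the last dose or on Day 85, whichever comes first, and the patient is then off study. Section 5.1 says that every subject is assessed after 12 weeks.

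**The concern.** By Section 3.3, the product of this pilot is the size and spread of the VO2peak decline in each arm, for use in designing a more definitive study. Those figures come from completers only. Loss may be related to the outcome: Section 8.8.1 lists adverse events, abnormal test results and progression among the grounds for withdrawal. Replacement restores the number of patients but not the missing outcomes.

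The plan's safeguard is LOCF. If LOCF can move away from the completer figure for reasons unconnected with how lost patients fared, or cannot respond to them at all, then neither agreement nor disagreement between the two tells the designers of the next study much.

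**Working it through.** **Inputs from the documents.** Section 11.6: variance 3.2 at each visit, correlation 0 or 0.20, 15 evaluable per arm, two-sided 0.05, 20% dropout, 36 accrued for 30 evaluable. Table 3: the visit days above. Section 5.1: 4 weeks on and 2 off, or 2 on and 1 off. **Assumed for illustration:** completers' mean change -2.0, carried interim changes of -1 to -4, and the deltas in step 5 (all ml/kg/min).

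**1. The plan's own figure.** SD of change = sqrt(2 × 3.2 × (1 - r)). At r = 0 this is 2.53; the detectable change with n = 15 and 80% power (noncentral t) is 1.97, stated as 2.0. At r = 0.20 the SD is 2.26 and the detectable change 1.76, stated as 1.8. Both reproduce. At r = 0, SE = 2.53/sqrt(15) = 0.653, and the 95% half-width is 2.145 × 0.653 = 1.40.

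**2. Fraction lost, q.** Going from 36 to 30 is 6/36 = 1/6, or 3 of 18 per arm. The stated rate is 0.20. Both are carried through.

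**3. LOCF for echo and muscle CSA.** With no interim value, a lost patient's last value is baseline, so the imputed change is 0:

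LOCF mean = (1 - q) × completer mean + q × 0

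This is 0.833 × the completer mean at q = 1/6, and 0.80 × at q = 0.20. No assumed decline is needed. If only post-baseline values may be carried, LOCF simply equals the completer result. Neither version responds to what happened to lost patients.

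**4. LOCF for VO2peak.** The interim CPET falls the day after the last planned dose (Day 28 on 4/2, Day 35 on 2/1). The last planned dose before Day 85 is Day 70 on 4/2 and Day 77 on 2/1, so Day 85 follows 14 or 7 planned days off drug. Suppose loss is unrelated to decline, so that the true mean is -2.0 and the completer mean is unbiased. With q = 1/6:

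| Three lost patients | LOCF mean | Error |
|---|---|---|
| all baseline-only | 5/6 × (-2.0) + 0 = -1.67 | +0.33 |
| one baseline-only, two carry -1 | (-30 - 2)/18 = -1.78 | +0.22 |
| one baseline-only, two carry -4 | (-30 - 8)/18 = -2.11 | -0.11 |
| all carry -4 | 5/6 × (-2.0) + 1/6 × (-4) = -2.33 | -0.33 |

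The first and last rows are extremes; at q = 0.20 they become -1.60 and -2.40.

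**5. How far lost patients could move the answer.** If they differ from completers by delta, the all-patient mean is -2.0 + q × delta and the variance is 6.4 + q(1 - q) × delta². At q = 1/6:

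| Delta | Mean | SD |
|---|---|---|
| +1 | -1.83 | 2.56 |
| 0 | -2.00 | 2.53 |
| -1 | -2.17 | 2.56 |
| -2 | -2.33 | 2.64 |
| -4 | -2.67 | 2.94 |

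The largest variance ratio is 8.62/6.4 = 1.35. At q = 0.20 and delta -4, the mean is -2.80.

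**6. What a repeated-measures model adds.** At r = 0, keeping all 18 baselines gives SE = sqrt(3.2/15 + 3.2/18) = 0.63, against 0.65 for completers. In a simulation of one arm at r = 0.20 the figures were 0.57 and 0.58. The gain is small, so the delta analysis has to carry most of the weight.

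**7. Off-study calendar.** Last dose + 30 < 85 gives a last dose on Day 54 or earlier. Allowing for the ±3-day window on Day 85 (earliest Day 82), last dose + 30 < 82 gives Day 51. The cut-off is thus about Day 51 to 54, before the ±7-day window on the End of Treatment Visit itself is considered.

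**The case against.** The strongest reply is that little turns on this. The complete-case choice is declared, the paired t-test can stay, and every illustrated shift is smaller than 1.40. The largest variance ratio, 1.35, is modest beside sampling error: with 15 patients, the 95% interval for a variance runs from 0.54 to 2.49 times the estimate. The ±0.33 errors need all three lost patients to be of one kind, and nothing in the documents supports an interim value of -4. All of this stands and limits the weight of the point. It does not make LOCF informative.

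A second reply is that the random effects model in Section 11.5 already uses interim values. It does, for non-completers who have a Day 29/36 CPET. But it targets the schedule effect, its outcome is change from baseline so that baseline-only patients contribute nothing, and no visit term is listed. Reporting losses and reasons by arm (Section 11.3) discloses the loss but gives no Day 85 change under another assumption.

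Third, not every key secondary measure is affected as echo and CSA are. Table 3 gives muscle strength and endurance an interim measurement, although the list in Section 8.5 does not. That is correct.

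A reader might also infer that early stoppers are barred from the Day 85 CPET. The documents are in tension rather than clear: Section 5.1 has all subjects assessed after 12 weeks, and Section 8.7 asks for reasonable effort to complete assessments in those lost to follow-up. By Day 51 or 54, 37 or 40 of the 56 planned dosing days have passed in each arm, but these are dosing days, not patients, and do not say how many will be lost.

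**Conclusion.** The point holds as a weakness in the sensitivity analysis. For echo and CSA it needs no assumption beyond q: carrying baseline forward gives 5/6 or 0.8 of the completer mean. For VO2peak, LOCF can err in either direction even under harmless loss. In the illustration the error ranges from +0.33 to -0.33 at q = 1/6 (±0.40 at 0.20) at the extremes, and from +0.22 to -0.11 in a mixed case.

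Two stronger readings are not supported. One is that the primary result is biased in a known direction or would reverse: the documents give no VO2peak data on lost patients and do not say how the 20% dropout arises, and an observed -2.0 stays significant across the illustrated range. The other is that LOCF always understates decline: that holds for baseline-only patients, but not where an end-of-dosing value worse than the Day 85 value is carried. What is affected is the mean and SD handed to the next study. This is a cheap improvement worth making, held with medium confidence.

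**What to change.** Keep the completer paired t-test as primary. In Section 11.5, replace LOCF with:

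1. The within-arm Day 85 change from a repeated-measures model with baseline as one of the outcomes and with visit and schedule-by-visit terms. Use the same form with two visits for echo and muscle CSA. Patients who were dosed and later replaced stay in.
2. A delta-adjusted analysis in both directions for non-completers relative to completers, for example +1 to -4 ml/kg/min for VO2peak. That range is an assumption for the investigators to settle beforehand; echo and CSA need ranges in their own units.

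The cost is text in Section 11.5, with IRB approval under Section 12.6; it needs no new visits or patients. The downside is wider intervals in the delta analysis and little information to work with at about three losses per arm.

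Separately, reconcile Section 5.1 with Sections 8.7, 8.8.2 and Table 3, so that it is clear whether a patient whose last dose is by about Day 51 to 54 is assessed after 12 weeks. Additional testing is not part of this fix: such patients may be off study and off drug, and their Day 85 values could answer a different question.

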## 11.2 Subject Demographics and Other Baseline Characteristics

Demographics and baseline characteristics will be summarized for the ITT population. Mean, median, standard deviation, minimum, and maximum will be displayed by treatment arm for continuous variables. Categorical variables will be summarized by counts and percentages for each arm.

## 11.3 Treatments

Compliance with sunitinib will be described, for each treatment arm, by the number and percent of intended doses taken (dose intensity). Deviations from the planned sunitinib schedule (i.e., 4/2 vs. 2/1) will be presented by numbers and percent of patients. In addition, the number and percent of patients having delays or dose reductions will be displayed by treatment arm.

Numbers of patients discontinuing treatment and reasons for discontinuation will be displayed for each treatment arm. Numbers of patients failing to complete full follow-up (through week 12) and reasons for loss to follow-up will be displayed for each treatment arm.

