### 3.3 Study Purpose/Rationale

#### *Schedule 2/1: An Important Alternative Dosing Regimen of Sunitinib*

A key challenge with sunitinib therapy for mRCC is to maximize quality of life (QOL) by minimizing toxicity without compromising efficacy. Specifically, maintenance of sunitinib dose intensity is related to improved clinical outcomes. A recent Phase III trial provides an example of these difficulties: fatigue was one of the most common treatment-emergent adverse events (AEs), with 63% of sunitinib-treated patients experiencing fatigue, including 17% with grade 3/4 fatigue. Interestingly, 49% of sunitinib-treated patients required dose interruptions of  $\geq 7$  days, and 51% required dose reductions; 20% discontinued treatment due to AEs. More work is clearly needed to achieve this delicate balance.

Preliminary evidence suggests that the alternative schedule 2/1 of sunitinib may maximize both efficacy and tolerability. In theory, schedule 2/1 (2-weeks on, 1-week off) results in more frequent dose interruptions than the standard schedule 4/2 (4-weeks on, 2-weeks off) without affecting dose intensity over the same six-week period. In practice, however, schedule 2/1 may achieve better dose intensity. Multiple retrospective studies comprising over 700 patients have suggested that switching from the standard 4/2 schedule to the alternative 2/1 schedule is associated with both improved outcomes and toxicity profile. Four sets of observations may explain these findings.

- First, maximizing the dose intensity of sunitinib is associated with improved clinical outcomes (PFS and OS).
- Second, both steady state of sunitinib and optimal inhibition of vascular perfusion are reached after 2 weeks.
- Third, an increased compensatory angiogenic response (proliferation of endothelial cells) has been associated with increased time off of sunitinib therapy.
- Fourth, AEs such as fatigue were typically the impetus for dose/schedule modification from schedule 4/2 in the retrospective studies. AEs improved with modification, potentially resulting in fewer dose interruptions and discontinuations due to toxicity.

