Exploratory	To evaluate safety and tolerability of both: (a) Sunitinib and (b) Exercise testing	Eligibility rate, attrition rate, and adverse event rate (CTCAE v4.0) in each arm	See Section 11.5
Exploratory	To determine the dose intensity of sunitinib	Patient- reported drug diaries	See Section 11.5
Exploratory	To estimate early change in VO 2 peak at 4-5 weeks compared with baseline	Change in VO 2 peak from baseline to 4-5 weeks	See Section 11.5
Exploratory	To collect plasma angiome samples for analysis and correlation with primary and key secondary endpoints	Plasma angiome multiplex ELISA	See Section 11.5
Exploratory	To use real-time electronic monitoring to describe the following over the study period (subset of patients): 
 
(a) Changes in daily physical activity
 
(b) Changes in daily blood pressure
 
	
 
(a) Steps per day
 
(b) Daily blood pressure (mmHg) reading
 
	See Section 11.5

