#### 5.1.1 Dose Modification

Dose interruptions or reductions of sunitinib may be required following potential drug-related toxicities. Fatigue, generalized muscle weakness, mucositis/stomatitis, hypertension, hand-foot syndrome, bleeding, vascular thrombosis, thrombocytopenia/neutropenia, and other AEs have been reported in response to treatment with sunitinib.

At each visit during the Treatment Period, subjects should first be evaluated for the occurrence of AEs and laboratory abnormalities. Specific recommendations for management of possible AEs, other than hepatotoxicity, along with guidelines for dose delay/modification or discontinuation of study treatment, are adapted from Kollmannsberger et al., and are provided in **Table 1**. In the event of treatment-emergent hepatotoxicity, please follow the guidelines for management hepatotoxicity provided in **Table 2**. For toxicities unrelated to sunitinib, dose modifications and holds are per the discretion of the investigator.

If dose reduction is necessary, two dose reductions are permitted in a stepwise fashion (initially to 37.5 mg and subsequently to 25 mg if necessary); however, the schedule (4/2 vs. 2/1) will not be changed during the study period. If the toxicity does not recur or worsen, the dose can then be increased stepwise back to the next dose level (37.5 mg or 50 mg as appropriate) at the start of the next treatment cycle. Increases to the next dose level should only be initiated at the start of the next treatment cycle, not during a treatment cycle.

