2. Sunitinib dose should be reduced by 12.5 mg (i.e., 50 mg to 37.5 mg or 37.5 mg to 25 mg), but the schedule (i.e., 4/2 or 2/1) MUST be maintained.

3. See **Section 5.2.1** for additional guidelines on management of fatigue and generalized muscle weakness.

4. Adverse events are graded according to NCI Common Terminology Criteria for Adverse Events v4.0

Abbreviations: SBP, systolic blood pressure; DBP, diastolic blood pressure; BP, blood pressure.

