### 5.4 Rationale for Selection of Dose, Regimen, and Treatment Duration

Sunitinib has an indication for the treatment of advanced RCC. The FDA-approved dose of sunitinib for advanced RCC is one 50 mg oral dose taken once daily, on a treatment schedule of 4 weeks on followed by 2 weeks off (schedule 4/2), which is the dose that will be used in **Arm A** for this study.

Sunitinib packaging (4/2015) states, "In patients with advanced RCC who are unable to tolerate Schedule 4/2, consider the dose reduction described in the FDA-approved label or, as an alternative, consider modifying the schedule to 2 weeks on treatment followed by 1 week off (Schedule 2/1) using the same dose.

—"Studies supporting Schedule 2/1 have not been reviewed by the FDA. For most studies, the patient population was small and/or analysis was post hoc, and therefore susceptible to bias. The efficacy of any particular alternative dosing schedule has not been established."

<https://www.pfizerpro.com/product/sutent/advanced-rcc/dosing#dm>

Schedule 2/1 will be used in **Arm B** for this study. **Note:** The dose intensity for a 6-week period is the same for schedule 4/2 and 2/1 (50 mg/day \* 28 days = 1400 mg).

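### Dose intensity is defined as a count of doses, so a mg reduction alone cannot lower it; the acceptance rate is divided by patients randomised, so it cannot fall below 100%

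*Combined protocol and SAP*

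**What the plan says.** Section 11.3 sets the compliance analysis: "Compliance with sunitinib will be described, for each treatment arm, by the number and percent of intended doses taken (dose intensity". It adds that "the number and percent of patients having delays or dose reductions will be displayed by treatment arm".

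Section 5.4 uses the same term for an amount of drug: "The dose intensity for a 6-week period is the same for schedule 4/2 and 2/1", followed by the arithmetic 50 mg per day for 28 days, 1400 mg.

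Section 5.1.1 says that "two dose reductions are permitted in a stepwise fashion (initially to 37.5 mg and subsequently to 25 mg if necessary". Footnote 2 of Table 1 gives the reduction as 12.5 mg per step, "but the schedule (i.e., 4/2 or 2/1) MUST be maintained".

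Section 4 lists as an exploratory objective "To determine the dose intensity of sunitinib", with patient drug diaries as the endpoint. Section 3.3 explains the interest: "In practice, however, schedule 2/1 may achieve better dose intensity".

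On participation, Section 11.5 says: "Acceptance rate is defined as the number of patients agreeing to participate divided by total number randomized". It also defines an eligibility rate as eligible patients over patients approached, and glosses that ratio as the screen failure rate. Under Section 8.1 consent comes before any screening procedure. Under Sections 5.3.3 and 8.3 randomisation comes after eligibility and baseline exercise testing.

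**The concern.** The protocol gives one term two meanings: mg over time in Section 5.4 and a count of doses in Section 11.3. The count is the one that will be reported. Toxicity can reduce exposure in two ways, through doses not taken and through smaller doses. The count registers only the first.

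This matters for the stated rationale. Section 3.3 suggests that schedule 2/1 may deliver better dose intensity in practice, and cites a trial in which 51% of sunitinib-treated patients needed a dose reduction. If one arm needs more or longer reductions, the measure named for the objective will not show the mg lost.

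The acceptance rate has a simpler fault. Its denominator is a subset of its numerator, so it says nothing about willingness to take part. What it reflects is how many consenting patients were later not randomised. The eligibility ratio is likewise not a screen failure rate, because a larger eligible fraction makes it rise.

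**Working it through.** **Inputs.** Dose levels of 50, 37.5 and 25 mg (Section 5.1.1); schedules of 4 weeks on and 2 off, or 2 weeks on and 1 off (Section 5.1); a 12-week period, Days 1 to 84; 15 evaluable patients per arm and 36 accrued (Section 11.6).

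**The plan's own figure.** Schedule 4/2: 28 × 50 = 1400 mg per 6 weeks. Schedule 2/1: 2 × 14 × 50 = 1400 mg. Section 5.4 is reproduced.

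**Planned over 12 weeks.** Schedule 4/2: 28 + 28 = 56 doses. Schedule 2/1: 4 × 14 = 56 doses. Either way 56 × 50 = 2800 mg.

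**Scores.** Count score = doses taken / 56. Mg score = mg taken / 2800.

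| Illustrative patient | Count score | Mg score |
|---|---|---|
| 28 doses at 50 mg, 28 at 37.5 mg, none missed | 56/56 = 100% | (1400 + 1050)/2800 = 87.5% |
| 28 at 50 mg, 14 at 37.5 mg, 14 at 25 mg, none missed | 56/56 = 100% | (1400 + 525 + 350)/2800 = 81.25% |
| 28 at 50 mg, 7 held, 21 at 37.5 mg | 49/56 = 87.5% | (1400 + 787.5)/2800 = 78.1% |
| 49 at 50 mg, 7 missed, no reduction | 49/56 = 87.5% | 2450/2800 = 87.5% |

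The two scores agree when doses are only missed. They separate as soon as the mg per dose is cut.

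**Arm level.** Assume that each reduced patient follows the first row and that no one misses a dose. The arm mean by mg is 1 − f × 0.125, where f is the fraction reduced.

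- 3 of 15 reduced: 1 − 0.200 × 0.125 = 97.5%.
- 8 of 15 reduced: 1 − 0.533 × 0.125 = 93.3%.

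The difference is 4.2 percentage points by mg and zero by count, since both arms score 100%. The fractions and the timing are assumptions.

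**Duration of a reduction.** Section 5.1.1 allows re-escalation only at the start of the next cycle, and a cycle is 6 weeks on 4/2 and 3 weeks on 2/1. One full cycle at 37.5 mg with no dose missed costs 28 × 12.5 = 350 mg (12.5% of 2800) on 4/2, and 14 × 12.5 = 175 mg (6.25%) on 2/1. Each patient scores 100% by count, and each appears as one patient with a reduction.

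**Acceptance rate.** Every randomised patient has consented, so consented ≥ randomised and consented / randomised ≥ 1. Take 36 randomised; the consent counts are assumed because the documents give none:

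- 36 consented: 36/36 = 100%, the minimum.
- 40 consented: 40/36 = 111%.
- 45 consented: 45/36 = 125%.
- 51 consented: 51/36 = 142%.

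If those 45 consenters came from an assumed 60 to 90 patients approached, consented / approached would be 75% to 50%.

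**The case against.** The strongest reply is that reductions are already reported. Section 11.3 tabulates patients with delays or reductions by arm, so the arm-level example above would appear there as 20% against 53%. That is right, and the count is not the only information the reader will have. The table gives neither the depth nor the duration of a reduction, however, and so no amount of drug lost.

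A second reply is that the no-missed-dose cases are favourable. Table 1 generally reaches a lower dose by way of an interruption, so many reduced patients will also lose doses and score below 100%. This stands as a limit on the size: the third row of the table shows a gap of 9.4 points (87.5 − 78.1) rather than 12.5. An interruption can also overlap the scheduled off period, so a reduced patient may miss no dose. In either case the reduction itself adds nothing to the count score.

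Third, the plan does not define an intended dose. If a reduced capsule did not count as one, the score would move, but it would then treat 37.5 mg as zero, which is no closer to mg. Section 11.5 also promises descriptive statistics for exploratory endpoints in general. A mg summary is thus not excluded, but nothing specifies one.

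Fourth, the data may be thinner than the fix assumes. Section 5.3.1 mentions only missed doses in the diary, Section 6.5 marks accountability as not applicable, and no log of patients approached is described. This stands as something to confirm.

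**Conclusion.** The concern holds, and it is minor. As written, a dose reduction alone leaves the Section 11.3 score unchanged. In the illustrated patients the count exceeds the mg score by 9.4 to 18.75 points. In the assumed no-missed-dose comparison of 3 against 8 reduced patients out of 15, a 4.2-point difference between arms does not show in this measure. These sizes depend on assumed timing and frequency of reductions; the defect in the definition does not.

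The acceptance rate has a floor of 100% whatever the counts, because consent precedes randomisation. The screen failure label on the eligibility rate is wrong.

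All of these are exploratory or descriptive measures. The primary VO2peak analysis, the sample size and the dosing rules are untouched.

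**What to change.** In Section 11.3, define relative dose intensity as total mg taken over Days 1 to 84 divided by the originally planned 2800 mg, and summarise it by arm. Count held and skipped doses as 0 mg and keep them in the denominator. State explicitly that, with this fixed denominator, doses not taken after permanent discontinuation also count as 0 mg. Keep the percent of intended doses taken as a separate compliance measure, and keep the existing tables of delays and reductions.

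In Section 11.5, define the acceptance rate as patients consenting divided by patients approached, and delete the screen failure label from the eligibility rate. At the same time, reconcile the terms: Section 4 lists an attrition rate, while Section 11.5 defines an acceptance rate instead.

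The cost is analysis wording in two sections, with no new assessment. Before analysis, the sponsor should confirm that the date and level of each dose change are recorded alongside the diary. It should also confirm that the number approached, which the eligibility rate already needs, is being logged.
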